15.2. Have any identifiable data/specimens been de-identified for use in this research study?
 No **Yes:** *If yes, describe how you will prevent any re-identification.*

15.3. Identify where data/specimens will be stored (e.g., on campus at Harvard or remotely, in a specimen laboratory) and describe the provisions to maintain confidentiality (e.g., password protection, encryption, locked filing cabinets, etc.). Refer to the [Investigator Manual](#) and the [Harvard Research Data Security Policy](#) for additional information.

Data from the Survey will be stored in real time in the Survey’s secure database. We use a US-based dedicated Windows hosting server running on an AWS EC2 Instance. The Root storage and File are handled by a Windows Server 2019 through IIS service. We also use an SQL Server 2017 for database. Finally, unique 2048-bit SSH-2 RSA key pairs are utilized to access the server and database

15.4. Indicate whether any data/specimens will be transferred/transmitted and describe the plan to share the data/specimens (e.g., outside of Harvard, to other researchers, to collaborators). Indicate who may request access and how. If data/specimens will be transferred/transmitted/shared, describe how, when, and to whom.

The Survey data will be maintained securely and will not be shared with any external parties. Data summaries will be generated for reports and publications.

15.5. Indicate whether participants' permission will be obtained to share their data/specimens and/or use their data/specimens in other future research projects.

No, there is no plan to share their data.

15.6. Indicate who is responsible for data/specimen management and how the research team and/or other collaborators are permitted access to information.

The Investigators are responsible for the conduct of the Survey and data management. Any potential collaborator or students/fellows working with the investigators would have access only to de-identified analytic files for specific analysis. At this point, there are no students working on this but if they join this project they would be supervised by the investigators and we will notify the IRB as needed.

15.7. Indicate how long data/specimens will be stored and describe the plans at the end of the storage period (e.g., are data/specimens destroyed, returned to data/specimen provider, etc.).

Data will be most relevant during the COVID pandemic, but maybe useful for many years (depending on COVID-19 development), the de-identified data will be most likely stored for many years.

16. Data/Statistical Analyses Plan

16.1. Describe plans for analysis (including the statistical method, if applicable).

The analysis will describe the wellness and mental health status of pregnant women during the COVID-19 pandemic. The distributions of mental health scales will be stratified by socio-demographic, healthcare access and COVID-19 characteristics. Descriptive tables will display, as appropriate, medians, ranges, means, standard deviations, and percentages.

16.2. Is there a sample size/power calculation?

No **Yes:** *If yes, describe the calculation and the scientific rationale, and, if applicable, by site and key characteristics such as participant demographics.*

Not applicable, we will recruit all eligible participants that fill out the online questionnaire.

17. Costs and Compensation **N/A.** *Skip to next section.*

17.1. Identify any costs that participants may incur during the study, including transportation costs, childcare, or other out-of-pocket expenses.

17.2. Identify remuneration that participants may receive during the study. Specify the amount, timing of disbursement, and method (e.g. money, gift cards, in-kind, incentives, raffles, and transportation). Describe how compensation will be calculated and paid if a participant withdraws. If any participant will receive a single payment more than \$100, or \$600 or more in one calendar year, refer to [Harvard University Financial Policy on Human Subject Payments](#).

18. Sharing Study Results N/A. *Skip to next section.*

18.1. Describe the plan to share study results with individual participants, the participant group/community, and/or others.

Results from the Survey will be reported at the aggregate level and presented at scientific meetings. Publications and presentations will be prepared by the Investigators.

19. Research Related Injuries N/A. *Skip to next section.*

19.1. Describe plans for medical care and compensation for research-related injuries.

20. Reportable Events

20.1. Outline plans for communicating reportable events to the IRB, Sponsor, or others as applicable (e.g., adverse events, unanticipated problems involving risks to participants or others, breach of confidentiality).

NA, de-identified data.

Any data breaches or participant complaints will be reported to the IRB within 5 business days.

21. Regulatory Compliance

21.1. Describe plans for monitoring regulatory compliance. The monitoring plan should include how you will ensure proper record keeping, retention of required regulatory documents and participant files, and adherence to the IRB-approved protocol and/or IRB policies and procedures. Monitoring plans should describe 1) who is responsible for file maintenance, 2) what will be maintained, 3) how often files will be reviewed and using what method, and 4) where documentation will be retained (for both Regulatory Documents and Participant files).

The Investigators are responsible for file maintenance (e.g., IRB documentation). Regarding records with patient information: The online survey will not collect identifiers. Data will be reviewed regularly to produce monthly reports using aggregate measures. Please see data security procedures above.

22. Data or Biospecimen Sharing N/A. *Skip to next section.*

If you plan to establish a repository, please submit a separate application using the [HLC Repository Protocol Template](#).

22.1. Describe the plan to send data/specimens to research collaborators outside of Harvard.

N/A

22.2. Describe the plan to receive data/specimens from collaborators outside of Harvard.

N/A

23. Clinical Trials N/A. *Skip to next section.*

Complete this section for clinical trials, including [NIH funded clinical trials](#) or [applicable clinical trials \(ACT\)](#) under the [FDA Amendments Act](#). To determine if a study meets the definition of a clinical trial, follow the guidance in the “Preparing the Research Protocol” section of the *Investigator Manual*.

23.1. Describe plans for registering this project in a clinical trials registry, e.g., clinicaltrials.gov. If available, provide the registry record number.

23.2. Describe plans for posting the clinical trial consent form on a publicly available federal website per federal requirements in the Common Rule (45§46.116(h)).

24. Device *This section should be completed if the study involves the use of any device on/in/with human subjects. N/A. Skip to next section.*

24.1. Describe the device, including the generic or common name, brand name (if applicable), purpose, function/operation, and whether it is an implant. Indicate who is providing this device for research use.

24.2. Indicate the FDA status of the device as it is being used for the proposed research:

- FDA-approved device being used “on-label” (i.e., FDA-approved purpose, population, manner).
- FDA-approved device that is being used “off-label” (i.e., for a different purpose, population, or in a different manner than approved).
- Not approved by the FDA.

24.3. Indicate the IDE Status of this device:

- The use of this device has an IDE.
- The use of the device qualifies for an Abbreviated IDE.
- The use of the device is exempt from the IDE requirements.

24.4. Has the FDA made a determination as to whether the device is Significant Risk or Non-Significant Risk? No Yes: *If yes, indicate the FDA’s determination.*

24.5. Describe plans for storage control, and dispensing of the product so that (1) only authorized investigators will use the product; (2) the product will only be used in participants who have provided consent, and (3) there will be documented tracking of each product, including unique identifiers and any return/disposal.

25. Drug/Biologic *This section should be completed if the study involves the use of any drug/biologic on/in/with human subjects. N/A. Skip this section.*

25.1. Describe the drug or biologic, including the generic or common name, brand name (if applicable), dosing, route of administration, number of doses, timing of administration. Indicate who is providing the drug, biologic, supplement for research use.

25.2. Indicate the IND Status of this drug or biologic and who holds the IND:

- There is an IND approval from the FDA for the use of this item.
The IND is held by:
- An IND application has been, or will be, submitted to the FDA.
The IND will be held by:
- An IND approval is not required.

25.3. Describe how dispensing, delivery and administration will be performed, and by whom. Include information about control (e.g., locked storage), tracking (e.g., lot number, returned pills), documentation, storage, and return/disposal.

Title: Health and Wellbeing of Pregnant and Post-Partum Women During the COVID-19 Pandemic

Document: Statistical Analysis Plan

NCT number: 04385238

Date: 04 May 2020

An anonymous, online, cross-sectional survey targeting pregnant and postpartum women will be conducted in 64 countries between May 26 2020 and June 13 2020. Participation in this study will be voluntary. All potential participants will be informed about the research objectives and standards of confidentiality regarding the use of the data. The survey, hosted on the Pregistryplatform for COVID-19 studies (<https://corona.pregistry.com>), will be advertised predominantly in social media channels and online parenting forums. Advertisements and the survey will be available in twelve languages (Arabic, Chinese, English, French, German, Italian, Korean, Portuguese, Russian, Spanish, Turkish, and Urdu) by human translators. We will seek to obtain at least 100 responses from each of the countries with the highest number of COVID-19 cases at the time of recruitment. Interested participants will be invited to follow a link to take the survey. The survey will collect standard demographic data and included questions that addressed topics such as COVID-19 exposure and worries, lifestyle changes, media exposure, protective factors, and mental health.

Participants. Women who self-identified as being 18 years or older at the time of the survey and as currently pregnant or having given birth within the past 6 months will be eligible to participate. The study was classified exempt by the Harvard Longwood Campus Institutional Review Board (HLC IRB) per the regulations found at 45 CFR 46.104(d)(2) on the basis that it poses no greater than minimal risk and that the recorded information cannot readily identify the subject (directly or indirectly).

Measures

COVID-19 Assessments

COVID-19 Exposure. Questions assessing whether participants were tested, diagnosed, or in contact with an individual who had COVID-19 will be adapted for this study based on those formulated by the US Centers for Disease Control and Prevention for the Household Pulse Survey.

COVID-19 Information Seeking. Participants will be asked about the frequency (never, <1x/day, 2-4x/day, 5-8x/day, 9-16x/day, and >16x/day) of their interactions with various sources of information, including the news, social media, and interpersonal discussions about COVID-19 using a measure modified from other published studies. For analyses, interactions will be categorized as never, <1x/day, 2-4x/day, 5+x/day.

COVID-19 Worries. Participants will be asked to rate their overall level of worry about COVID-19 on a Likert Scale ranging from 1 for “not worried at all” to 4 for “very worried”. They will be then asked to endorse fifteen specific worries on a list developed for this study. Exploratory factor analyses will be conducted to identify domains within the questionnaire, with oblimin rotation on a tetrachoric correlation matrix due to the binary nature of the variables. Worries will be categorized into the following domains: social (parents/grandparents unable to visit, family unable to visit, not able to have a baby shower, not able to attend a funeral), COVID-19 infection-related (participant or partner will bring infection home, family or friends will get COVID-19), child-related (no adequate childcare, other children will get COVID-19), delivery-related (partner not present during delivery, changes to delivery plan, unborn baby will get COVID-19, not able to breastfeed), economic (significantly affect economic situation/finances), and missing doctor appointments.

COVID-19 prevention behaviors. Participants will be asked to endorse seventeen behaviors they had engaged in to protect themselves from COVID-19 from a list developed for this study based on WHO recommendations and media reports. Behaviors will be classified into the following categories: hygiene-related (mask-wearing, washing hands, disinfecting surfaces), physical distancing (avoiding public places, restaurants and other people, canceling personal engagements, work or school and

working at home), canceling travel (for work or pleasure), stockpiling essential resources (food or water, hand sanitizer, medication), postponing medical care, and prayer.

Mental Health Outcomes

Depression and Anxiety will be assessed via the Patient Health Questionnaire-4 (PHQ-4) a four-item inventory rated on a four-point Likert-type scale. Items are drawn from the first two items of the 'Generalized Anxiety Disorder-7 scale' (GAD-7) and the 'Patient Health Questionnaire-8' (PHQ-8). The overall PHQ-4 score is a sum of the four items (0 = not at all, 1 = several days, 2 = more than half the days, 3 = nearly every day). A PHQ-4 score of ≥ 6 is considered clinically significant.

Posttraumatic stress symptoms will be assessed via a modified version of the Impact of Events Scale - 6 (IES-6). Participants will be asked to report how bothered they will be by each symptom from 0 (Not at all) to 4 (Extremely) over the past seven days. The symptom statements will be modified to assess impact related to the COVID-19 pandemic. The scale is scored by calculating the mean of the five items used in this study, with the original IES-6 cutoff score of 1.75 yielding 0.88 sensitivity and 0.85 specificity for posttraumatic stress disorder (PTSD) diagnosis. Loneliness will be evaluated using the UCLA Three-Item Loneliness Scale (UCLA-3). Participants are asked how often they experience the following: feeling that they lack companionship, feeling left out, and feeling isolated from others. Questions will be framed so that participants described their feelings since the start of the COVID-19 pandemic. Responses are rated as 1 (Hardly Ever), 2 (Some of the Time), or 3 (Often), with the overall score as the sum of the three responses. A score of 3 is considered low, 4-5 medium, and ≥ 6 high. High loneliness has been associated with poorer mental and physical health over the life course.

Sociodemographic factors and potential confounders

Standard socio-demographic measures will be collected including age, education (categorized as never attended school, elementary school, some high school, high school graduate or general equivalency diploma (GED), some college/university, college diploma or university degree, master's degree, professional degree, doctoral degree), self-identified race/ethnicity (categorized as White/Caucasian, Latina/Hispanic, Asian, South Asian, Black, Middle Eastern, Native Hawaiian or Other, Pacific Islander, American Indian or Alaska Native, Other/Multiracial), employment status (healthcare worker in a hospital or clinic, worked in a nursing home, essential/key worker (as defined by the government), none of these, don't know), medical coverage status, marital status (married, living with partner, divorced, separated, single, widowed), weeks pregnant/postpartum (first trimester 0 to <13 weeks, second trimester 13 to <28 weeks, third trimester 28+ weeks, postpartum). Participants indicated their country of residence which was classified by region for analytic purposes.

Statistical analyses

Descriptive statistics for socio-demographic characteristics, COVID-19 exposure variables, mental health, and loneliness will be calculated by perinatal stage, classified as first, second, or third trimester, or post-partum, for all participants. A series of multivariable logistic regressions will be then run to test the study hypotheses. For these analyses, PHQ-4, IES-6 and UCLA-3 outcomes will be specified as binary dependent variables using recommended cutoffs. The first set of models included pregnancy stage, socio-demographic variables and COVID-19 exposure as independent variables. The second set of models examined the type and amount of information seeking about COVID-19 as independent variables. The third and fourth set of models focused on COVID-19 worries and COVID-19 behaviors as independent variables. Models for information seeking, COVID-19 worries, and

COVID-19 behaviors will be adjusted for age, level of education, race, survey region, marital status, and pregnancy stage.

Models will be estimated using the GLM function in the R statistical program, version 3.6.2. Due to the number of models run, interpretations are focused on effects that met the threshold of $p < .001$. Due to low levels of missingness (667 [9%]) a complete case analysis was conducted. The raw data used for the study are publicly available.

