5.2. Does the study involve more than one participant group?

No **Yes:** *If yes, identify each group here and throughout all applicable sections.*

Pregnant women will be the only participants enrolled. No question will be asked about babies.

5.3. Indicate the duration of a participant’s involvement.

Participants will complete a single online survey (20 min approximately). There will be no follow up.

- 5.4. Indicate the total number of participants to be screened (if applicable) and/or enrolled (i.e., signed consent form). If the proposed research involves secondary data analyses only, indicate the number of data, documents, records, and/or specimens that will be obtained.**

We expect to receive responses from around 5000 women. If we launch quickly.

- 5.5. List inclusion and exclusion criteria, including age ranges of all participants, and describe the screening process.**

To be eligible for this study women must:

- (1) be 18 years of age or older,
- (2) self-identify as pregnant or recently pregnant (within the last 6 months),
- (3) be fluent in the English language, and
- (4) have access to a computer, tablet, or smartphone with an Internet connection.

The study population will consist of volunteers from any country in the world except European countries/those covered by GDPR.. It is expected that the Registry participants will represent a wide range of maternal age, race/ethnic background, and health status given the ubiquitous presence of smartphones and high-speed Internet connectivity among millennials (18 to 34 years of age) and Gen X (35 to 46 years of age).

Regarding the screening, when women click to participate in the Survey they will confirm the inclusion criteria above.

- 5.6. Describe study procedures.**

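### The child-related worry odds ratio pools women who have no other children with mothers who are not worried, and is biased if having other children is related to the outcome.

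*SAP*

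**What the plan says.** SAP, Measures, COVID-19 Worries: "They will be then asked to endorse fifteen specific worries on a list developed for this study". The factor analysis uses a "tetrachoric correlation matrix due to the binary nature of the variables", so each item is endorsed or not endorsed. One resulting domain is "child-related (no adequate childcare, other children will get COVID-19". No not-applicable response is described.

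SAP, Statistical analyses: "The third and fourth set of models focused on COVID-19 worries and COVID-19 behaviors as independent variables". The outcomes are binary PHQ-4, IES-6 and UCLA-3. Models for information seeking, worries and behaviours "will be adjusted for age, level of education, race, survey region, marital status, and pregnancy stage". Interpretation focuses on effects with p<.001.

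SAP, Sociodemographic factors and potential confounders: the list opens "Standard socio-demographic measures will be collected including age, education" and goes on to race/ethnicity, employment, medical coverage, marital status, pregnancy stage and country. Parity, or other children at home, is not named. Eligibility is not restricted by parity, and no subgroup of mothers is defined. Protocol section 16.1 plans only descriptive tables and does not address the point.

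**The concern.** Only a woman who already has a child can meaningfully endorse the item about other children becoming infected. The childcare item applies mainly to such women, although a first-time mother could endorse it for the coming or new baby. With binary coding and no restriction, a first-time mother who leaves both items blank is coded like a mother of three who is not worried.

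The coefficient then compares worried mothers with a mixture of unworried mothers and women without other children. Any association between having other children and the outcome enters it in part. This is plausible for loneliness, which asks about companionship and isolation. A larger sample does not reduce the bias; it only narrows the interval around the wrong value. A spurious association could be reported, or a real one hidden, for one worry domain across three outcomes.

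**Working it through.** The documents give no odds ratio, prevalence or power figure for this point, so there is nothing to reproduce. The calculation below shows what the plan's coding would produce under stated assumptions.

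**From the documents.** The SAP reports missingness of 667 (9%). If 9% refers to all respondents, the total is 667/0.09 = 7,411 and complete cases are 7,411 − 667 = 6,744. Rounding of the 9% allows 6,354 to 7,180. The threshold is p<.001; taken as two-sided (the SAP does not say), |z| must exceed 3.29.

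**Assumed, not in the documents.** First-time mothers 45%; worry endorsed by 50% of the other women and by a share e = 0 or 10% of first-time mothers; outcome prevalence p0 among women without other children from 10% to 45%; an OR for having other children on the outcome (parity OR, θ); worry OR of 1.0 within each group. The domain is scored as any item versus none, because the SAP does not state the scoring.

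**Step 1, who is in the reference group.** With e = 0, non-endorsers are 0.45 first-time mothers plus 0.55 × 0.5 = 0.275 unworried mothers. First-time mothers are 0.45/0.725 = 62% of the group. With e = 10% the share is 0.405/0.680 = 60%.

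**Step 2, one case in full (p0 = 0.30, e = 0, θ = 1.5).**
- Outcome odds in mothers: (0.30/0.70) × 1.5 = 0.643, so the risk is 0.391.
- Endorsers are all mothers: risk 0.391.
- Non-endorsers: (0.275 × 0.391 + 0.45 × 0.30)/0.725 = 0.335.
- Pooled OR: (0.391/0.609)/(0.335/0.665) = 1.28, although worry has no effect.
- SE of the log OR: √[1/(6,744 × 0.275 × 0.391 × 0.609) + 1/(6,744 × 0.725 × 0.335 × 0.665)] = 0.056; z = 4.35.

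On the log scale, ln(1.278)/ln(1.5) = 0.61, so about 61% of the parity association is carried over.

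**Step 3, the same formulas over the assumed range, N = 6,744.**

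| p0 | e | θ = 1.5: OR (z) | θ = 0.67: OR (z) |
|---|---|---|---|
| 10% | 0 | 1.27 (2.96) | 0.77 (−2.53) |
| 10% | 10% | 1.19 (2.27) | 0.83 (−1.94) |
| 30% | 0 | 1.28 (4.35) | 0.77 (−4.00) |
| 30% | 10% | 1.20 (3.33) | 0.83 (−3.06) |
| 45% | 0 | 1.29 (4.59) | 0.78 (−4.46) |
| 45% | 10% | 1.20 (3.52) | 0.83 (−3.41) |

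With θ = 1.25 the OR is 1.10 to 1.15, and with θ = 0.8 it is 0.87 to 0.90; the largest expected |z| is 2.5, below 3.29. With θ = 1.0 it is exactly 1.00. If 20% of first-time mothers endorse, at p0 = 30% and θ = 1.5, it falls to 1.14 (z = 2.42). At the 5,000 responses expected in Protocol section 5.4, every z is multiplied by √(5,000/6,744) = 0.86.

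**Step 4, masking.** With a true worry OR of 1.5, p0 = 30%, e = 0 and θ = 0.67, the pooled OR is 1.16 (z = 2.47), and a real association misses the threshold. With θ = 1.5 it is 1.92.

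**Step 5, does age adjustment remove it?** In 300 simulated logistic fits at N = 6,744, with age correlated with having other children and no worry effect, the age-adjusted OR was 0.79 for θ = 0.67 (69% of fits at p<.001) and 1.26 for θ = 1.5 (80%). With a term for other children the ORs were 1.01 and 1.00, and no fit reached p<.001. The strength of the age correlation was assumed.

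**The case against.** The strongest reply is that the questionnaire is not in the documents. The socio-demographic list is introduced with the word including and need not be complete. Parity may have been asked, or the item shown only to mothers. This stands: a reader might infer that parity was never collected, and the documents do not show that. The adjustment list, however, is explicit and omits it, and no restriction is stated.

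The size is also uncertain. No document gives an association between parity and any outcome. The bias is zero if there is none, and moderate associations (1.25 or 0.8) would not be expected to pass p<.001. A reader might infer from the 45% prevalence row, with no first-time mother endorsing, that a false positive is near certain. That is close to a worst case: at 10% prevalence, or with 20% of first-time mothers endorsing at 30% prevalence, even a parity OR of 1.5 has an expected z below 3.29. The three outcomes need not share one prevalence.

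Age, marital status and stage are partial proxies for having children. The age-adjusted simulation suggests that the protection is small, but the table is unadjusted, and the SAP does not say whether domains enter jointly.

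Two further readings fail. Protocol section 5.2 says "No question will be asked about babies", which might seem to rule out asking about children. It answers whether there is a second participant group and says nothing about parity or older children. Nor does the argument extend to the information-seeking and behaviour models, whose predictors do not presuppose other children.

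**Conclusion.** The concern holds as a conditional one. The plan as written does not separate child-related worry from having children to worry about, and its OR is biased in either direction if having other children is related to the outcome. Under the stated assumptions, parity ORs of 1.5 and 0.67 move a true null to about 1.19 to 1.29 and 0.77 to 0.83, with |z| of about 1.9 to 4.6. The p<.001 threshold is therefore not a dependable safeguard, but a false finding is not assured either. The direction and size in this survey cannot be known from the documents. The point affects one domain in the third set of models and should be corrected; it does not undermine the other analyses.

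**What to change.** Use a yes/no item on other children if the survey has one, or add it if the survey is not yet fielded. The SAP date precedes the stated survey window, but the SAP also reports observed missingness, so which case applies must be established. Then, in the third set of models, either:

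- estimate the child-related worry association only among women with other children; or
- use a three-level predictor: no other children; children, not worried; children, worried. The comparison of interest is between the last two levels.

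State how the domain is scored. If the item was not collected, report the child-related domain descriptively, or state that its OR cannot be read as an effect of worry.

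The cost is SAP wording and at most one survey item. The worry contrast also rests on fewer women: under the 45% assumption, about 0.55 × 6,744 = 3,709.

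### Women with no job, studies or travel plans cannot endorse the travel, work and school behaviors, and the behavior models do not identify them, so those odds ratios may be confounded

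*SAP*

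**What the plan says.** **SAP, Measures, COVID-19 prevention behaviors.** The instrument is a checklist: "Participants will be asked to endorse seventeen behaviors they had engaged in to protect themselves from COVID-19". The behaviors are then grouped. Physical distancing covers avoiding public places, restaurants and other people, then "canceling personal engagements, work or school", and also working at home. Canceling travel is a separate category: "working at home), canceling travel (for work or pleasure". The answer options are not given, and no rule says whether a category is scored as any, all, a count or single items.

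**SAP, Statistical analyses.** "The third and fourth set of models focused on COVID-19 worries and COVID-19 behaviors as independent variables". The adjustment list reads "COVID-19 behaviors will be adjusted for age, level of education, race, survey region, marital status, and pregnancy stage". On multiplicity, "interpretations are focused on effects that met the threshold of" p < .001.

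**SAP, Sociodemographic factors and potential confounders.** Work is recorded as "employment status (healthcare worker in a hospital or clinic, worked in a nursing home, essential/key worker (as defined by the government), none of these", plus a don't-know level. Student status and travel plans are not among the listed measures.

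**The concern.** On an endorsement list, a woman who had no trip to cancel gives the same response as a woman who had one and kept it. The same holds for canceling work or school and for working at home when there is no job or course. The non-endorsing group is then a mixture of women who could have acted and did not, and women who could not act.

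The planned covariates do not separate the two. Adding the employment item as listed would not do so either, because its residual level pools ordinary workers with women who have no job.

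If women without work, studies or travel plans differ in depression and anxiety, posttraumatic stress or loneliness after adjustment, the odds ratio for the behavior partly measures that difference. A precaution could look protective, or harmful, with no association among the women able to take it. The p < .001 threshold is a response to the number of models. It does not remove bias, and a sample of several thousand makes a moderate bias easy to detect as an effect.

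**Working it through.** The documents give no effect size, power or prevalence for the behavior models, so there is no planned figure to reproduce. The check asks how large a false association could be.

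**Inputs from the documents**
- N: the protocol (section 5.4) expects about 5,000 women. Less the SAP's 9%, that is 5,000 × 0.91 = 4,550 complete cases. The SAP's own statement, "Due to low levels of missingness (667 [9%]) a complete case analysis was conducted", implies 667 / 0.09 = 7,411 women and 7,411 − 667 = 6,744 complete cases.
- Threshold: .001, taken as two-sided, critical value 3.29.

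**Assumed inputs**
- Share unable to do the act: u = 30% (also 15% and 45%).
- Endorsement among those able: e = 60%.
- Outcome prevalence among those able: p = 25%, the same whether or not they endorse, so there is no true behavior effect.
- R: odds ratio for the outcome, unable versus able, remaining after the listed covariates.

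**Formulas**
- Prevalence in women unable: q = Ro / (1 + Ro), with o = p / (1 − p) = 1/3.
- Prevalence in all non-endorsers: m = [(1 − u)(1 − e)p + uq] / [1 − (1 − u)e].
- False odds ratio: OR = [p / (1 − p)] / [m / (1 − m)].
- SE of log OR: √{1 / [n₁p(1 − p)] + 1 / [n₀m(1 − m)]}, with n₁ endorsers and n₀ non-endorsers.
- Chance of p < .001: Φ(|log OR| / SE − 3.29) + Φ(−|log OR| / SE − 3.29).

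**One case in full (R = 1.5, N = 4,550)**
- n₁ = 4,550 × 0.7 × 0.6 = 1,911; n₀ = 2,639.
- q = 0.5 / 1.5 = 0.333.
- m = (0.28 × 0.25 + 0.30 × 0.333) / 0.58 = 0.293.
- OR = 0.333 / 0.415 = 0.80; log OR = −0.218.
- SE = √(1/358.3 + 1/546.8) = 0.068; ratio 3.21.
- Chance = Φ(3.21 − 3.29) = 47%.

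**u = 30%, both sample sizes**

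| R | m | False OR | Chance, N = 4,550 | Chance, N = 6,744 |
|---|---|---|---|---|
| 0.67 | 0.215 | 1.22 | 31% | 54% |
| 1.0 | 0.250 | 1.00 | 0.1% | 0.1% |
| 1.25 | 0.273 | 0.89 | 6% | 12% |
| 1.5 | 0.293 | 0.80 | 47% | 73% |
| 2.0 | 0.328 | 0.68 | 99% | about 100% |

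At N = 4,550 and R = 1.25, 1.5 and 2.0, u = 15% gives 1%, 9% and 57%; u = 45% gives 12%, 73% and about 100%.

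The same formulas apply to canceled travel, with u the share of women with no travel planned. Both travel acts need a trip, so no scoring rule avoids the problem there.

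**The mixed distancing category.** I took seven items, four that need no job or studies and three that do. That count is consistent with the stated seventeen: 3 hygiene + 7 distancing + 2 travel + 3 stockpiling + 1 postponed care + 1 prayer. Logistic models were simulated with N = 4,550, u = 30%, R = 1.5, endorsement probability .75 for the four general items and .5 for the three work items among women able to do them.
- Seven-item count: p < .001 in about 40% of runs (38% to 46% across repeated simulations), per-item OR about 0.92.
- Any/none: 0%. The share scoring zero is 0.3 × 0.25⁴ + 0.7 × 0.25⁴ × 0.5³ = 0.15%, about 7 women, so the predictor is nearly constant and its estimate too imprecise to pass.
- Four general items only: OR 1.00, p < .001 in about 0.3%. This follows from simulating those items as unrelated to work status; it does not prove that they are.
- Work/school items as a predictor of their own, without eligibility data: 75% to 80% as a count, 92% to 95% as any. Separating these items without knowing who could do them makes the bias worse.
- Work items fitted only among women able to do them: 0% to 0.3%.

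**The case against.** The strongest reply is that the SAP is silent rather than wrong. The questionnaire is not in the documents, so a not-applicable option may exist on the form. Protocol sections 12.1 and 14.1 let women skip questions, and the SAP does not say whether a blank counts as no or as missing. A reader might infer that women without a job or trip are definitely coded as failing to take the precaution. The text does not establish that; it is the natural reading of an endorsement list with nothing further described.

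Second, the bias needs a residual association between ability and outcome after education, region, marital status and the other covariates. The documents give no figure and do not fix its sign. At R = 1.0 there is no excess over 0.1%. This stands, and it is why the table runs from no effect to large and includes the opposite direction.

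Third, the distancing category may be scored any/none, in which case it is hardly affected. This also stands, but the SAP does not commit to that rule, and the reply does not reach canceled travel.

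Fourth, the line between general and work-dependent acts is a judgment: canceling personal engagements requires having some. That is fair. The proposed distancing predictor is therefore described only as items that do not need a job or studies.

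**Conclusion.** The point holds as a conditional one. The canceled-travel category can be endorsed only by women with travel planned, and no planned covariate identifies them. Its odds ratio is confounded, in either direction, if having such plans is related to the outcome after adjustment. The distancing odds ratio shares the problem under count or item-level scoring and hardly at all under any/none scoring.

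The size rests wholly on assumed shares and residual odds ratios. With 30% unable and N = 4,550, it runs from nothing at a residual odds ratio of 1.0, through a 6% chance of passing the threshold at 1.25, to about an even chance at 1.5 and near certainty at 2.0. The larger N implied by the SAP's missingness figure raises these chances.

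A reader might go further and conclude that any behavior effect reported at p < .001 is false. The documents do not support that: they neither show the residual association nor state the scoring rule. The concern is limited to the work, school and travel items in the fourth set of models and to how those results may be interpreted.

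**What to change.** 1. Before the survey opens on 26 May, add a 'did not apply / none planned' answer to the work, school and travel items.
2. Fit the behavior models for those items among women to whom they applied, or use three levels: done, not done, not applicable.
3. Build the physical-distancing predictor from the items that do not need a job or studies (avoiding public places, restaurants and other people; canceling personal engagements), and state its scoring rule in the SAP.
4. If the form cannot be changed, still use that distancing predictor. Report both the travel and the work/school items descriptively, as done versus not done or not applicable, and interpret neither as a precaution effect. Do not enter the work/school items as a separate predictor without eligibility data, since that is the most biased option.

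The cost is one more response option on a few items, in twelve languages, possibly with a change from a tick list to per-item answers; fewer women in the work, school and travel models; and a few lines in the SAP. The fallback needs no new data, which matters because protocol section 4.3 describes the online collection as ready.
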